2.1.2.1 Rescue therapy

Except for SGLT2 inhibitors and thiazolidinediones, any approved medication(s) including oral antidiabetic drugs or insulin can be prescribed to treat the hyperglycemia at the discretion of the investigator. Rescue therapy is considered a noninvestigational medicinal product (NIMP).

2.1.2.2 Prohibited prior and concomitant medications

During the study, the following medications are prohibited:

- Initiation of any antidiabetes agents, including oral or injectable antihyperglycemic agents other than the IMP and NIMP is not allowed before the rescue therapy. The existing background medication (NIMP) should not be modified before the rescue.

Note: short term use (<10 consecutive days) of the prohibited medication, eg, short-acting insulin for treatment of acute illness or surgery is allowed.

- SGLT2 inhibitors (eg, canagliflozin, dapagliflozin, or empagliflozin) and thiazolidinediones (eg, pioglitazone, rosiglitazone) are not allowed for rescue.
- Systemic use of glucocorticoids for more than 10 consecutive days within 90 days prior to the Screening Visit (Note: topical, intra-articular, ophthalmic, nasal spray, or inhaled applications are allowed).
- Investigational medication products in any other clinical study
- Modification of antihypertensive medication before Week 12 is not allowed unless for safety reasons.
- Initiation of any weight loss drugs (eg, phentermine, orlistat, lorcaserin, phentermine/topiramate, naltrexone/bupropion, liraglutide).
- Initiation of medication known to affect bone mass or modify the risk of fractures:
 - Bisphosphonates, selective estrogen receptor modulators (SERMs), calcitonin, teriparatide, denosumab, strontium ranelate, growth hormone,
 - Androgen deprivation therapy,
 - Aromatase inhibitors,
 - Anticonvulsants (eg, carbamazepine, phenytoin and phenobarbital),
 - Hormone replacement therapy (systemic or transdermal) that includes estrogens or androgens.

Reduction of digoxin dose should be considered because sotagliflozin acts as a weak P-gp inhibitor and increases systemic exposure to digoxin.

Other medications which are unlikely to interfere with the pharmacokinetics (PK) or pharmacodynamics (PD) of the IMP or confound interpretation of the study endpoints are allowed as needed following discussion between the Investigator and the Sponsor/CRO.

The dose of all antihypertensive agents should be kept constant during the 12 weeks following Randomization and no antihypertensive agents should be added or withdrawn for the 12 weeks following randomization unless it is considered necessary for safety reasons.

It is recommended that patients receiving calcium or vitamin D at the time of screening, or initiating supplementation during the study, should maintain as stable a dose as possible throughout the study. Patients receiving replacement therapy with estrogen or testosterone for more than 24 months at the time of screening should also be advised to maintain stable dose for the duration of the study, unless if required for safety reasons.

2.1.3 Efficacy endpoints

All efficacy measurements collected during the study will be considered for analyses, including those obtained after IMP discontinuation or introduction of rescue therapy (see [Section 2.5.4](#)).

HbA1c, FPG, UACR, eGFR and serum estradiol are measured/calculated in a central laboratory (see study flowchart in Appendix D). Body weight, SBP and DBP (see [Section 2.1.4.5](#)) are measured at on-site visits by the investigator. Patients requiring rescue are identified as those with the reason for treatment ticked “rescue therapy” in e-CRF “Medication” page.

Efficacy variables will be summarized in both standard international units and conventional units when applicable.

2.1.3.1 Primary efficacy endpoint(s)

The primary efficacy endpoint is the change from Baseline to Week 26 in HbA1c (%) comparing sotagliflozin 400 mg versus placebo.

2.1.3.2 Secondary efficacy/safety endpoint(s)

2.1.3.2.1 Key Secondary safety endpoint(s)

The key secondary safety endpoint is the percent change from Baseline to Week 26 in BMD (lumbar spine, total hip, and femoral neck).

Analysis of key secondary safety endpoints are detailed in [Section 2.4.5.1](#) .

2.1.3.2.2 Secondary efficacy endpoint(s)

The main secondary efficacy endpoints are:

- Change from Baseline to Week 26 in HbA1c (sotagliflozin 200 mg only).
- Change from Baseline to Week 26 in BW.
- Change from Baseline to Week 26 in FPG.
- Change from Baseline to Week 12 in SBP for all patients.
- Proportion of patients with HbA1c <7.0% at Week 26.

2.1.3.3 Other efficacy endpoint(s)

The other secondary efficacy endpoints are:

- Change from Baseline to Weeks 52 and 104 in HbA1c.
- Change from Baseline to Weeks 52 and 104 in FPG.
- Change from Baseline to Weeks 52 and 104 in BW.
- Proportion of patients with HbA1c <7.0 % at Weeks 52 and 104.
- Proportion of patients starting rescue therapy during the 104 weeks of treatment.
- Change from Baseline to Weeks 26 and 104 in SBP for all patients.
- Change from Baseline to Weeks 12, 26, and 104 in SBP for the subsets of patients with Baseline SBP <130 mmHg and \geq 130 mmHg, respectively.
- Change from Baseline to Weeks 12, 26, and 104 in DBP for all patients and the subsets of patients with Baseline DBP \geq 80 mmHg and <80 mmHg, respectively.
- Change from Baseline to Weeks 26, 52, and 104 in total body fat mass and total lean mass measured by DXA.
- Change from Baseline to Weeks 26, 52, and 104 in serum estradiol (only for women).
- Change from Baseline to Weeks 26, 52, and 104 in UACR.
- Change from Baseline to Weeks 26, 52, and 104 in eGFR.

2.1.4 Safety endpoints

The safety analysis will be based on the reported adverse events, hypoglycemia, adjudicated bone fractures, and other safety information, such as BMD data measured by DXA, clinical laboratory data (including bone turnover markers and markers of calcium metabolism), vital signs, electrocardiogram (ECG), and physical examination, etc.

The following safety endpoints will be assessed throughout the 104 weeks of double-blind treatment:

- Adverse events, hypoglycemia (all, severe, and/or documented symptomatic hypoglycemia), EOSI, adverse events of special interest (AESI), AEs leading to discontinuation of IMP, SAEs, and deaths.
- Percent change from Baseline to Weeks 26, 52 and 104 in BMD (lumbar spine, total hip, and femoral neck).
- Proportion of patients with adjudicated bone fractures over 104 weeks.
- Proportion of patients with \geq 3% decline in BMD at Week 104.
- Changes from Baseline in bone turnover markers to Week 26, 52, and 104 (serum bone resorption markers: N-terminal telopeptide of Type 1 collagen [NTX] and β -CTX-1; serum bone formation markers: P1NP and osteocalcin).

- Changes from Baseline in markers of calcium metabolism to Week 26, 52, and 104 (serum: calcium, phosphorus, magnesium, parathyroid hormone [iPTH], 25-hydroxyvitamin D and 1,25-dihydroxyvitamin D; urinary: calcium, phosphorus and magnesium).
- Clinical laboratory results, vital signs results, and 12-lead ECG.

Observation period

The observation period starts from the time when the patient gives informed consent and will be divided into 4 epochs:

- The **screening** epoch is defined as the time from the signed informed consent date up to the first administration of the double-blind IMP.
- The **treatment** epoch is defined as the time from the first administration of the double-blind IMP to the last administration of the double-blind IMP. This epoch includes the 26-week double-blind core treatment period and the 78-week double-blind extension treatment period. The 26-week double-blind core treatment period is the time from the first administration of double-blind IMP to the last administration of double-blind IMP on or before Visit 8/Week 26 (or Day 182 if Visit 8/Week 26 date is missing).
- The **residual treatment** epoch is defined as the time from the last administration of the double-blind IMP up to 10 days (1 day for hypoglycemia) after the last administration of the double-blind IMP.

The treatment-emergent adverse event (TEAE) period will include both **treatment** and **residual treatment** epochs. (See the TEAE period for the 26-week core treatment period in [Section 2.5.4](#)).

- The **posttreatment** epoch is defined as the period of time starting the day after the end of the treatment-emergent adverse event period up to the last protocol-planned visit or the resolution/stabilization of all serious adverse events (SAE), adverse events of special interest (AESI) and events of special interest (EOSI), whichever is later.

The **on-study observation period** is defined as the time from start of double-blind treatment until the end of the study (defined as the last scheduled visit for those who completed the study and the date collected on e-CRF page “Completion of End of Study/Follow-up” for those who did not complete the study).

The **post-study observation period** is defined as the time from the day after the end of the study until the resolution/stabilization of all SAE, AESI and EOSI if applicable.

2.1.4.1 Hypoglycemia

Hypoglycemia will be identified as events recorded on the dedicated e-CRF “Hypoglycemic event information” page, and will be categorized as follows (see study protocol for further details):

Severe hypoglycemia

Severe hypoglycemia is an event requiring assistance of another person to actively administer carbohydrate, glucagon, intravenous glucose or other resuscitative actions. These episodes may be associated with sufficient neuroglycopenia to induce seizure, unconsciousness or coma.

Self-monitored plasma glucose values may not be available, but neurological recovery attributable to the restoration of plasma glucose to normal is considered sufficient evidence that the event was induced by a low plasma glucose concentration.

Severe hypoglycemia is identified in e-CRF “Hypoglycemic event” page as those documented as,

1. To the question “Countermeasure Administration”, ticked the option “Subject was Not Capable of Treating Self and Required Assistance”, and
2. To the question “Were Symptoms Present”, ticked “Yes”.

Documented symptomatic hypoglycemia

Documented symptomatic hypoglycemia is an event during which typical symptoms of hypoglycemia accompanied by a measured plasma glucose concentration of ≤ 3.9 mmol/L (≤ 70 mg/dL).

Clinical symptoms that are considered to result from a hypoglycemic episode are eg, increased sweating, nervousness, asthenia/weakness, tremor, dizziness, increased appetite, palpitations, headache, sleep disorder, confusion, seizures, unconsciousness, or coma.

Documented symptomatic hypoglycemia is identified in e-CRF “Hypoglycemic event” page as those documented as,

1. To the question “Countermeasure Administration”, NOT ticked the option “Subject was Not Capable of Treating Self and Required Assistance”, and
2. To the question “Were Symptoms Present”, ticked “Yes”, and
3. With a plasma glucose value before countermeasure ≤ 3.9 mmol/L (≤ 70 mg/dL).

Asymptomatic hypoglycemia

Asymptomatic hypoglycemia is an event not accompanied by typical symptoms of hypoglycemia but with a measured plasma glucose concentration ≤ 3.9 mmol/L (≤ 70 mg/dL).

Asymptomatic hypoglycemia is identified in e-CRF “Hypoglycemic event” page as those documented as,

1. To the question “Countermeasure Administration”, NOT ticked the option “Subject was Not Capable of Treating Self and Required Assistance”, and
2. To the question “Were Symptoms Present”, ticked “No”, and
3. With a plasma glucose value before countermeasure ≤ 3.9 mmol/L (≤ 70 mg/dL).

Probable symptomatic hypoglycemia

Probable symptomatic hypoglycemia is an event during which symptoms of hypoglycemia are not accompanied by a plasma glucose determination, (but that was presumably caused by a plasma glucose concentration ≤ 3.9 mmol/L [≤ 70 mg/dL]), ie, symptoms treated with oral carbohydrate without a test of plasma glucose.

Probable symptomatic hypoglycemia is identified in e-CRF “Hypoglycemic event” page as those documented as,

1. To the question “Countermeasure Administration”, NOT ticked the option “Subject was Not Capable of Treating Self and Required Assistance”, and
2. To the question “Were Symptoms Present”, ticked “Yes”, and
3. With no plasma glucose value before countermeasure, and
4. To the question “Did this countermeasure lead a significant improvement or prompt recovery?”, ticked “Yes”.

Relative hypoglycemia

Relative hypoglycemia, recently termed “pseudo-hypoglycemia” is an event during which the patient reports typical symptoms of hypoglycemia, and interprets the symptoms as indicative of hypoglycemia, but with a measured plasma glucose concentration > 3.9 mmol/L (> 70 mg/dL).

Relative hypoglycemia is identified in e-CRF “Hypoglycemic event” page as those documented as,

1. To the question “Countermeasure Administration”, NOT ticked the option “Subject was Not Capable of Treating Self and Required Assistance”,
2. To the question “Were Symptoms Present”, ticked “Yes”, and
3. With a plasma glucose value before countermeasure > 3.9 mmol/L (> 70 mg/dL).

In addition of the threshold of ≤ 3.9 mmol/L (≤ 70 mg/dL), hypoglycemia episodes with a plasma glucose of < 3.0 mmol/L (< 54 mg/dL) will be analyzed separately.

Any hypoglycemic event fulfilling the criteria of a SAE or leading to unconsciousness, coma, or seizure will also be recorded as a SAE (see [Section 2.1.4.2](#)).

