### **Observation period of safety endpoints**

The observation period of safety data will be divided into 3 segments:

- The pretreatment period is defined as the time between the date of the informed consent and the first dose of double-blind IMP.
- The treatment-emergent period (TEAE period) is defined as the time from the first dose of double-blind IMP up to 10 days (1 day for hypoglycemia) after the last dose of double-blind IMP, regardless of the introduction of rescue therapy. The 10-day interval is chosen based on the half-life of the IMP (approximately 5 times the half-life of sotagliflozin in patients with moderate renal dysfunction).
- The post-treatment period is defined as the time starting 11 days after the last dose of double-blind IMP (after the treatment-emergent period).

The Baseline value for safety endpoints in the safety population is the last available value prior to the first administration of the double-blind IMP.

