### Severe hypoglycemia

Severe hypoglycemia is an event requiring assistance of another person to actively administer carbohydrate, glucagon, intravenous glucose or other resuscitative actions. These episodes may be associated with sufficient neuroglycopenia to induce seizure, unconsciousness or coma. Self-monitored plasma glucose values may not be available, but neurological recovery attributable to the restoration of plasma glucose to normal is considered sufficient evidence that the event was induced by a low plasma glucose concentration.

**Note:** “Requiring assistance of another person” means that the patient could not help himself or herself to treat the hypoglycemia. Assisting a patient out of kindness, when assistance is not required, should not be considered a “requires assistance” incident.

Any hypoglycemic event which leads to unconsciousness, coma, or seizure should also be reported as an **SAE**.

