2.4.5.2 Analyses of hypoglycemia

Analyses of hypoglycemia will be performed on the TEAE period as defined in [Section 2.1.4](#). Hypoglycemia will be classified as severe hypoglycemia, documented symptomatic hypoglycemia, asymptomatic hypoglycemia, probable symptomatic hypoglycemia or relative hypoglycemia (See [Section 2.1.4.1](#)).

The number (%) of patients with 1) any hypoglycemia, 2) severe hypoglycemia and documented symptomatic hypoglycemia will be summarized respectively by treatment group during the TEAE period, as well as the incidence rate in patient years. Two types of incidence rates will be presented: the number of patients with event(s) per 100 patient-years (calculated as the number of patients with at least 1 event/ total exposure in 100 patient-years) and the total number of events per 100 patient-years (calculated as the total number of events / total exposure in 100 patient-years). Note: Note: here exposure in days is duration of treatment-emergent AE period, ie, duration of IMP treatment in days +1 ([Section 2.1.4](#)).

The summary of frequency and incidence rate in patient-years for severe hypoglycemia or documented symptomatic hypoglycemia will be provided as appropriate by gender, age group (≥ 55 to < 65 , ≥ 65 years), race (White, Black or African American, Asian, Other).

A KM curve will be provided by treatment group for the time to first severe hypoglycemia or documented symptomatic hypoglycemia during the TEAE period for the 104-week entire treatment period only (see [Section 2.4.5](#)).

Documented symptomatic hypoglycemia may be presented by ≤ 70 mg/dL (3.9 mmol/L) and < 54 mg/dL (3.0 mmol/L) respectively, as appropriate.

A listing of patients for all events reported on the dedicated e-CRF “Hypoglycemic event information” page will be provided with each category flagged (ie, severe hypoglycemia, documented symptomatic hypoglycemia, asymptomatic hypoglycemia, probable symptomatic hypoglycemia and relative hypoglycemia).

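### SAP 2.1.4.1 adds a symptom tick to the definition of severe hypoglycemia, so an assisted event with symptoms marked No or left blank falls in no category

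*SAP*

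**What the plan says.** Protocol 10.6.1 gives the definition: "Severe hypoglycemia is an event requiring assistance of another person to actively administer carbohydrate, glucagon, intravenous glucose or other resuscitative actions". It adds that glucose values may be missing and that neurological recovery once glucose is restored is enough evidence. SAP 2.1.4.1 repeats this definition.

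The SAP then says how to find these events on the hypoglycemia page of the e-CRF. Two conditions must both hold. The first is that the site "ticked the option “Subject was Not Capable of Treating Self and Required Assistance”, and"; the second is "To the question “Were Symptoms Present”, ticked “Yes". The documented symptomatic, asymptomatic, probable symptomatic and relative categories each start from the opposite condition, "NOT ticked the option “Subject was Not Capable of Treating Self and Required Assistance".

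SAP 2.1.4.2, Table 2, uses the same algorithm for the event of special interest and places it among the events that are not adjudicated. SAP 2.4.5.2 builds the hypoglycemia summaries, incidence rates, subgroup summaries and Kaplan-Meier curve on these categories. It also promises a listing of every event on the page, flagged by category.

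**The concern.** The algorithm is narrower than the definition it implements. Neither document makes a separate symptom report part of the definition of severe hypoglycemia. Because every other category shuts out assisted events, an event that fails the second condition has nowhere else to go.

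The outcome is a named event of special interest, and insulin-treated patients are eligible (protocol 7.1). Protocol 4.6 reports no severe hypoglycemia in completed sotagliflozin trials, so counts per arm are likely to be very small, and a single unclassified event can change what the table shows. No adjudication committee would catch it. The missing-data rules in SAP 2.5.3 do not cover a blank symptom item either, although they are conservative elsewhere: a missing relationship to study drug is assumed to be related, and an event with an incomplete onset date defaults to treatment-emergent.

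**Working it through.** The plan states no figure on this point, so there is none to reproduce. The check is to run every possible set of answers through the five definitions in SAP 2.1.4.1.

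**Inputs (the items the algorithms use):** assistance ticked or not (2); symptoms Yes, No or blank (3); glucose at or below 70 mg/dL, above 70 mg/dL, or not measured (3); recovery after the countermeasure Yes or No (2).

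- All combinations: 2 × 3 × 3 × 2 = 36.
- Combinations with assistance ticked: 3 × 3 × 2 = 18.
- Of these, severe under the SAP (symptoms Yes): 1 × 3 × 2 = 6.
- Of these, in any other category: 0, because all four require assistance not ticked.
- Assisted and unclassified: 18 − 6 = 12.

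| Assistance ticked, symptoms | Glucose ≤70 | Glucose >70 | No glucose |
|---|---|---|---|
| Yes | severe | severe | severe |
| No | none | none | none |
| Blank | none | none | none |

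The recovery item plays no part for assisted events. The 18 combinations therefore reduce to the 9 cells above, 3 severe and 6 unclassified. No combination meets two definitions. With classification on assistance alone, all 18 would be severe.

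**Where an unclassified assisted event goes:**

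- Severe summary and severe/documented summaries, with their rates and subgroups (SAP 2.4.5.2): lost.
- Kaplan-Meier curve for first severe or documented symptomatic event (SAP 2.4.5.2): lost.
- Severe hypoglycemia as an event of special interest (SAP 2.1.4.2, Table 2): lost.
- Any hypoglycemia (SAP 2.4.5.2): kept, if within the treatment-emergent period, since every event on the page counts as hypoglycemia.
- Listing: kept, but with no category flag to show.
- Serious adverse events: kept only if it qualifies, since "Any hypoglycemic event fulfilling the criteria of a SAE or leading to unconsciousness, coma, or seizure will also be recorded as a SAE".
- Separate analysis below 54 mg/dL: uncertain. SAP 2.1.4.1 words it for episodes in general, while SAP 2.4.5.2 describes it only for documented symptomatic events.

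**The case against.** The best counter-argument is that assistance ticked with symptoms No is close to a contradictory entry. The footnote to protocol Figure 1 puts the inability to self-treat down to acute neurological impairment. Both documents list confusion, seizures, unconsciousness and coma among the clinical symptoms. A patient found unresponsive is therefore symptomatic and should be ticked Yes; the item does not ask for recalled symptoms. Protocol 13.4 already provides for data queries. This stands, and it means that few events should be affected. It does not close the gap: no rule says what happens to an entry that stays No or blank, and if needing help already implies symptoms, the second tick adds nothing but a way to drop the event.

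A second objection is that assistance alone could label as severe an event with no symptoms and glucose above 70 mg/dL. That can happen after a mis-ticked box. A query is the right remedy, and protocol 10.6.1 already tells sites not to count help given out of kindness.

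A reader might also infer that the cut-off after the last dose is a second defect, because the treatment-emergent period runs "up to 10 days (1 day for hypoglycemia) after the last administration of the double-blind IMP". The 10 days are justified as "approximately 5 times the half-life of sotagliflozin in patients with moderate renal dysfunction", which implies a half-life of 10 / 5 = 2 days and 0.5^(1/2) = 71% of drug left at day 1. The documents do not support calling this an error. The protocol pre-specifies the 1-day window, and the SAP follows it consistently in the rate denominator and the censoring rules. The 71% applies to moderate renal dysfunction only; no half-life is given for other patients. A longer window would also take in events after other glucose-lowering therapy may have been changed, so the choice is a trade-off. Nor is a conflict with the serious-event tables shown, because the 1-day limit is written into the treatment-emergent period itself.

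**Conclusion.** The point holds for the classification rule. As written, an assisted event with symptoms No or blank is lost from every summary specific to severe hypoglycemia. In terms of answer patterns this is 12 of 18; in terms of events it is probably very few, and the documents give no frequency from which to estimate it. The conclusion rests on reading the two conditions as joint, which the wording requires, and on the e-CRF allowing an assisted event to be saved with symptoms No or blank. The documents do not describe an edit check that prevents this.

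It would go too far to say that the SAP removes severe hypoglycemia from its own tables. Correctly completed assisted events are classified as severe, and the others remain visible as any hypoglycemia and in the listing. The 1-day window is not part of this finding. At most, the SAP could state which window applies to hypoglycemia that is also recorded as a serious adverse event, since neither document says so explicitly.

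**What to change.** In SAP 2.1.4.1, identify severe hypoglycemia by the assistance item alone, whatever the symptom or glucose entry. The event-of-special-interest criterion in Table 2 then follows, because it points to the same algorithm. Query any assisted event with symptoms No or blank before each of the two database locks in SAP section 4. If the query is not resolved, keep the event as severe and mark it in the listing.

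The cost is a short SAP edit, one condition removed from the program, and one data query rule. The protocol needs no change, because the edit brings the SAP into line with protocol 10.6.1. The downside is small: an occasional wrongly ticked assistance item may be counted as severe.

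Optionally, add one line on the window for hypoglycemia recorded as a serious adverse event.
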